### 8.3 Off-Agent Criteria

Participants may stop taking study agent for the following reasons: completed the protocol-prescribed intervention, adverse event or serious adverse event, inadequate agent supply, noncompliance, concomitant medications, medical contraindication, or pregnancy. Participants will continue to be followed, if possible, for safety reasons and in order to collect endpoint data according to the schedule of events.

### 8.4 Off-Study Criteria

Participants may go ‘off-study’ for the following reasons: the protocol intervention is completed, AEs, SAEs, lost to follow-up, participant’s refusal of follow up, participant withdrawal (*e.g.*, due to toxicity unacceptable to the participant or the investigator), physician decision to take the participant off study, other reason (*e.g.*, determination of ineligibility including screen failure, non-compliance, pregnancy or medical contraindication), abnormal results of ECHO at baseline (defined as an ejection fraction less than the institution’s lower limit of normal), or death. Participants found to be ineligible during the screening phase and after signing the Informed Consent document and assigning the PID number, will be considered “screen failures”. Such participants will be taken off study and the appropriate end of study CRFs will be completed for these participants. In cases of early termination, when possible, participants

will be asked to return to the clinic site prior to going off study for an early termination visit according to the Schedule of Events.

## 8.5 Study Termination

NCI, DCP as the study sponsor has the right to discontinue the study at any time.

## 9. CORRELATIVE/SPECIAL STUDIES

### 9.1 Rationale for Methodology Selection

#### 9.1.1 Enumeration of nelipepimut-S-specific CTL

**Rationale.** MHC class I vaccines such as nelipepimut-S+GM-CSF are designed to stimulate clonal expansion of antigen-specific CTL. In a subset of 86 patients from our phase I/II trials investigating nelipepimut-S+GM-CSF, we used a dimer assay to quantify nelipepimut-S-specific CTL and found that only 1 of 30 (3%) patients with -specific CTL levels above the mean recurred compared to 8 of 56 (14%) with levels below the mean [21]. This suggests that robust *in vitro* immunologic responses may identify participants in whom vaccination will be efficacious. The primary objective of this trial is to evaluate the nelipepimut-S-specific CTL response in participants receiving NeuVax versus control participants receiving GM-CSF alone.

#### 9.1.2 Histologic Responses

**Rationale.** Because this trial will administer vaccines before surgical therapy, the effects of immunization will be assessed on residual tumor at the time of surgical resection. A previous trial investigating a HER2-targeting dendritic cell vaccine in participants with DCIS showed a decrease in the number of HER2-expressing tumor cells in residual DCIS lesions suggesting that vaccination had stimulated an immune response capable of eliminating the HER2+ clones within the tumor. Dendritic cell vaccines are limited by their complexity which requires leukapheresis to obtain an individual participant's blood from which dendritic cells can be isolated, matured, and stimulated with the antigen of interest at a central processing facility. Our peptide vaccine strategy is also capable of stimulating an antigen-specific immune response but has the obvious advantage of being much simpler as it is an "off the shelf" therapy. In order to determine the intratumoral immune response stimulated in response to vaccination, we will evaluate for: 1) HER2 expression, and 2) the degree of lymphocyte infiltration (determined on H&E stained slides as well as determined by multiplex immunofluorescence), .

### 9.2 Comparable Methods

The methodology described above are those previously used (see details above), and the resulting data will be able to be compared to existing data.

## 10. SPECIMEN MANAGEMENT

### 10.1 Laboratories

We plan to evaluate biomarkers in both PBMC and tissue specimens. For our primary biomarker, nelipepimut-S-specific CTL, we will use a dextramer assay, which is a flow cytometry based assay, to enumerate the number of nelipepimut-S-specific CTL generated in response to vaccination with the nelipepimut-S peptide. Phase I/II studies of NeuVax (= nelipepimut-S + GM-CSF) showed a correlation between nelipepimut-S-specific CTL and disease free survival [20]. Our tissue based assays will be performed in a CLIA certified laboratory (HER2 [32] and lymphocyte infiltration [assessed on hematoxylin & eosin stained slides] [33] and multiplex immunofluorescence will be analyzed in the laboratory of our pathology collaborator using established protocols .

#### 10.1.1 PBMC and serum samples

Dextramer Assay: to enumerate the number of nelipepimut-S-specific CTL	[name], DO, PhD The University of Texas MD Anderson Cancer Center
---	--

#### 10.1.2 Tissue samples

Histologic analysis (presence or absence of DCIS, invasive breast cancer, grade of tumor)	Breast Tumor Immunology Lab Dana Farber Cancer Institute
HER2	Breast Tumor Immunology Lab Dana Farber Cancer Institute
Multiplex Immunofluorescence	Laboratory of Systems Pharmacology Harvard Medical School PI: [name]
Immune infiltration in normal tissue maximally distant from the tumor (in mastectomy samples)	Undetermined* MD Anderson Cancer Center

\* In the mastectomy samples we will perform core needle biopsies of the normal tissue, maximally distant from the tumor (*ex vivo* after the mastectomy if performed) and store for future studies of immune infiltrates.

### 10.2 Collection and Handling Procedures

Random, blinded, unique ID numbers will be assigned to specimens at each time point and will be distributed with the PID numbers. All specimens will be labeled with the unique specimen number (XXXX), date and time specimen collected and protocol # MDA2014-04-02, at a minimum. Laboratories receiving the specimens will be blinded from distinguishing participant information and visit point but this information will be kept available in a password protected electronic log at each site to indicate which specimen number belongs to which participant and at what visit. The master log of specimen IDs will be kept at the Coordinating Center.

Multiple blood draws will be required for immunologic assessments in this trial. Approximately 70 mL will be drawn at each time point when blood is drawn for immunologic assessments. Participant blood samples labeled as described above will be sent from study sites via overnight delivery to the laboratory of [name], DO, PhD at MD Anderson where immunologic response assays will be performed. Assays will be run within 30 days of receipt of specimen. Blood not used to perform the dextramer assay will be frozen and stored in the laboratory of [name], DO, PhD under the unique protocol number and identifier for up to five years for additional immunologic studies related to this protocol. No genetic testing will be performed on this material. Study participants will not be contacted in the future for additional use of these stored blood specimens. If study participants want their blood specimens removed from storage and destroyed, they may do so by contacting the PI or research nurse or coordinator at any time. Additionally, any stored blood may also be utilized to assess new generations of vaccines.

For blood draws performed for immunologic assessment, 10 mL are collected into a BD Vacutainer Rapid Serum tube (BD, Franklin Lakes, NJ) which contain a clot activator and silicone coated interior. After centrifugation, serum will be collected, aliquoted in 1 mL vials and frozen for batch analysis. The samples will undergo a single freeze-thaw. The remaining 60 mL are collected into BD Vacutainer CPT Cell Preparation tubes which contain an anticoagulant (sodium heparin or sodium citrate) with FICOLL HYPaque density gradient fluid and a polyester gel barrier. The density gradient fluid and the gel barrier allow for the separation of PBMC from the red blood cells by a single step centrifugation process. The PBMC fraction will be collected by centrifugation and suspended in RPMI-1640 (GIBCO, Invitrogen Corporation, Carlsbad, CA) with 10% FCS (Gemini Bio-Products, West Sacramento, CA) and antibiotics. Cells will be counted, aliquoted at  $5 \times 10^6$  cells in 1 mL vials and either used to perform the indicated immunologic assays or frozen.

#### **10.2.1 Materials and Methods for nelipepimut-S-CTL Determination**

PBMC will be isolated by ficoll gradient and stained with aqua live/dead stain (Invitrogen) and the following antibodies: CD8 APC-H7 (BD Biosciences), CD3 PE Cy7 (BD Biosciences), nelipepimut-S -APC-conjugated dextramer (Immudex), and the following pacific blue conjugated lineage antibodies: CD4 (BD Biosciences), CD14 (BD Biosciences), CD16 (BD Biosciences), and CD19 (Biolegend). Cells will be analyzed on a LSR Fortessa Analyzer (BD Biosciences) and the number of nelipepimut-S-specific CTL will be determined.

#### **10.2.2 Immunohistochemistry (IHC)**

We will utilize standard IHC techniques to measure expression of specific biomarkers in tissue samples. Tissue samples will be required from both the initial breast biopsy and the subsequent surgical excisional procedure. An H&E stained slide and 10 unstained slides (or 11 unstained slides) from the initial breast biopsy and an H&E and 10 unstained slides (or 11 unstained slides) from the subsequent surgical excisional procedure should be sent to the Breast Tumor Immunology Lab at the address provided in **Section 10.3** below. The biopsy slides should be sent within 6 weeks of randomization. The slides from the surgical procedure should be sent within 6 weeks of the surgery. All slides can be sent at room temperature. The study pathologist will review all of the H&E slides as well as subsequent slides prepared for biomarker assessment and mark the relevant areas for evaluation. Standard antibody recognition techniques will be used to assess expression of specific biomarkers of interest listed below. Both positive and negative controls will be included in each batch to ensure the functionality of the antibody. We plan to assess the following biomarkers: HER2 and lymphocyte infiltration. Multiplex

immunofluorescence will be analyzed in the laboratory of our collaborator using established protocols.

In the mastectomy samples only we will perform core needle biopsies of the normal tissue, maximally distant from the tumor (ex vivo after the mastectomy if performed) and store for future studies of immune infiltrates. These core needle biopsy samples should be formalin fixed and paraffin embedded. The block or 10 unstained slides should be sent to the Breast Tumor Immunology Lab with the surgical samples at the address provided in Section 10.3.

### 10.4 Tissue Banking

Biologic specimens collected during the conduct of each clinical trial that are not used during the course of the study will be considered deliverables under the contract and thus the property of the NCI. At study completion, NCI reserves the option to either retain or relinquish ownership of the unused biologic specimens. If NCI retains ownership of specimens, the Contractor shall collect, verify and transfer the requested biologic specimens from the site to a NCI-specified repository or laboratory at NCI's expense.

## 11. REPORTING ADVERSE EVENTS

DEFINITION: AE means any untoward medical occurrence associated with the use of a drug in humans, whether or not considered drug related. An AE can therefore be any unfavorable and unintended sign), symptom, or disease temporally associated with participation in a study, whether or not related to that participation. This includes all deaths that occur while a participant is on a study.

Please note that all abnormal clinical laboratory values that are determined to be of clinical significance based on a physician's assessment are to be reported as AEs. Those labs determined to be of no clinical significance or of unknown clinical significance (per the physician's assessment) should not be reported as AEs. Any lab value of unknown clinical significance should continue to be investigated/followed-up further for a final determination, if possible.

An abnormal lab value should be deemed clinically significant if either of the following conditions is met:

- The abnormality suggests a disease and/or organ toxicity that is new or has worsened from baseline.
- The abnormality is of a degree that requires additional active management, e.g., change of dose, discontinuation of the drug, close observation, more frequent follow-up assessments, or further diagnostic investigation.

Therefore, a clinically significant lab value is one that indicates a new disease process, an exacerbation or worsening of an existing condition, or requires further action(s) to be taken.

A list of AEs that have occurred or might occur (Reported Adverse Events and Potential Risks) can be found in §6.2, Pharmaceutical Information, as well as the Investigator Brochure or package insert.

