## **6.9 Blinding and Unblinding Methods**

- 6.9.1 Participants will be blinded to NeuVax™ or GM-CSF alone arm assignment.
- 6.9.2 The Statistician, Site Study Pharmacist and other investigators will not be blinded to NeuVax™ or GM-CSF alone arm assignment.
- 6.9.3 Participants randomized to the nelipepimut-S/GM-CSF arm will receive two vaccinations of nelipepimut-S (1000 µg) and GM-CSF (250 µg) consisting of 4 intradermal inoculations two weeks apart prior to surgery. Participants randomized to the GM-CSF alone arm will receive inoculations of GM-CSF (250 µg) administered in an identical manner to those receiving nelipepimut-S/GM-CSF.
- 6.9.4 At the end of the study participants will be unblinded to their assignment.
- 6.9.5 Study agents may be unblinded during the course of the study if deemed medically necessary in the event of a serious adverse event after discussion with the NCI medical monitor. Unblinding will be conducted as follows:
  - 1) The Site PI contacts the Protocol Principal Investigator ([name], PhD) and requests the participant’s treatment status be unblinded.
  - 2) The Protocol Principal Investigator ([name], PhD) contacts the NCI DCP Medical Monitor ([name], MD) and requests the participant’s treatment status be unblinded. The Protocol Principal Investigator then conveys the Medical Monitor’s decision to the Site PI. The Site PI then proceeds with unblinding as written out below.
  - 3) If the NCI Medical Monitor cannot be reached and the participant requires emergency care, the Protocol Principal Investigator ([name]) may authorize the site PI to break the blind.
  - 4) If the Site PI is unable to reach the Protocol Principal Investigator and the participant requires emergency care, then the Site PI must proceed with unblinding as written out below.
  - 5) The Site PI officially unblinds the participant and takes the participant off-study.
  - 6) The date and reason for breaking the blind must be submitted by the Site PI to the Protocol Principal Investigator, [name], PhD as soon as possible.

- 7) It is the responsibility of the Protocol Principal Investigator to report the date and reason for breaking the blind to the NCI Medical Monitor, [name], MD as soon as possible after receiving this information from the Site PI.

NCI Medical Monitor:  
[name], MD  
NCI/Division of Cancer Prevention  
[name]  
[name]  
[name]  

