### **7.3.3 Day of Surgery (Day 28 +/-5 days):**

- Blood for immunologic assays will be drawn prior to the surgical procedure.
- Blood will be drawn for laboratory evaluations prior to surgery. Pre-surgery laboratory evaluations will include the following:
  - Platelets
  - Hemoglobin
  - Alkaline Phosphatase
  - Lactate Dehydrogenase
  - Bilirubin
  - AST (SGOT)/ALT (SGPT)
- Research tissue for tissue biomarkers (from the surgical specimen). For patients undergoing mastectomy, a representative sample of normal tissue maximally distant from the tumor will be obtained to assess for immune infiltrates.
- Adverse Events.
- Concomitant medications.
- Symptom assessment.

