## **13. STATISTICAL CONSIDERATIONS**

### **13.1 Study Design/Description**

This is a Phase II, randomized, single-blind study with 2 intervention arms. A total of 108 DCIS participants will be consented and screened for eligibility and, with a conservative estimate, 48 (45%) participants are expected to be HLA-A2 positive. These 48 participants will be randomized 2:1 to vaccine and GM-CSF alone groups. Accounting for 10% attrition rate while on study and for approx. 5% non-evaluable sample rate, we expect to have 40 evaluable participants, 27 in vaccine and 13 in GM-CSF alone group, that have all baseline, post-vaccination (pre-surgery), and post-surgery measures of nelipepimut-S-specific CTL. With 27 and 13 in vaccine and GM-CSF alone groups, respectively, we will have 82% power to detect an effect size of 1 on the change of nelipepimut-S-specific CTL ("1 month (+/- 7 days) after completion of the vaccination series timepoint" minus pre-1st vaccine) between the two groups, corresponding to change of  $0.05\% \pm 0.05\%$  in vaccine group and  $0 \pm 0.05\%$  in control group, using two-sided t-test with a significance level of 0.05.

The decision rule for declaring the agent promising will be if we detect an effect size of 1 on the change of nelipepimut-S-specific CTL, and if there are not greater than 10% grade III AEs attributed to the active

study drug or IV AEs of any attribution. Completion of the current study will provide the necessary data to determine the next phase of study, specifically whether a subsequent, larger phase II will be conducted versus a phase III study.

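### Section 11 gives opposite reporting instructions for an unresolved abnormal lab value, so lab toxicity can be under-counted and counted inconsistently

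*Combined protocol and SAP*

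**What the plan says.** Section 11 makes abnormal labs reportable as AEs when a physician judges them clinically significant. For the rest, it says that labs the physician finds to be of no significance, or of unknown significance, "should not be reported as AEs. Any lab value of unknown clinical significance should continue to be investigated/followed-up further for a final determination", where that is possible. The unresolved ones are thus kept out of the AE data while more work is asked for on them.

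The section then defines significance: "An abnormal lab value should be deemed clinically significant if either of the following conditions is met". The first condition is that the value suggests disease or organ toxicity that is new or worse than at baseline. The second is that the abnormality is of a degree that calls for additional active management, with examples that include "close observation, more frequent follow-up assessments, or further diagnostic investigation". A closing sentence widens this to any abnormality for which further action is required.

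On timing, 7.3.3 states: "Blood will be drawn for laboratory evaluations prior to surgery". The schedule in 7.1 allows this draw up to 5 days before surgery and shows no later safety labs. On use, 13.5 tabulates AEs by grade and relationship, 13.7 describes toxicities by arm, and 13.1 calls the agent promising only "if there are not greater than 10% grade III AEs attributed to the active" study drug, or grade IV AEs of any attribution. On blinding, 6.9.2 states: "The Statistician, Site Study Pharmacist and other investigators will not be blinded".

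**The concern.** A value of unknown significance is kept out of the AE data while it is being followed up. The same section says that a value which requires more follow-up or further diagnostic work is significant and belongs in the AE data. Two sites holding the same unresolved result can each point to section 11 and do opposite things.

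This matters because the analysis plan has no other place for such a result. Toxicity is summarised only through AEs, so a value held as unknown does not appear in the safety result unless someone later reclassifies it. The classification is a physician's judgement, and the investigators know the arm, so handling could differ by arm as well as by site. The toxicity profile is the first secondary objective (1.2.1), and AE counts form the safety half of the rule in 13.1.

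**Working it through.** No figure in the plan is in dispute. The check sets the text side by side and then bounds the exposure.

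1. **The two instructions.**
   - Not reported: unknown significance, on the physician's assessment, while follow-up continues where possible.
   - Reported: any value meeting either condition, where the second condition names closer observation, more frequent follow-up and further diagnostic investigation.
   - An unknown value that needs added follow-up or a diagnostic work-up falls under both. Section 11 gives no order of precedence, no date for the determination, no outcome if none is reached, and no exception by grade.

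2. **Does another section settle it?**
   - 7.4.1 and 7.5: no safety labs at the 30-day post-op visit or the final visit, so no scheduled draw resolves the question. Any repeat test is unscheduled.
   - 11.1.1.2: AE recording is specified up to the 30-day post-op visit, with no requirement to classify open labs by then.
   - 11.1.5: follow-up covers AEs, including labs the investigator finds clinically significant. The telephone call covers unresolved AEs with at least possible attribution. An unknown lab is in neither group.
   - 11.1.2: severity grade is a data element of an AE report, so a value not reported gets no grade there.
   - 13.5 and 13.7: AEs and toxicities only, with no separate lab summary.

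3. **Exposure.** Seven tests are taken both at baseline (7.2) and before surgery (7.3.3): platelets, haemoglobin, alkaline phosphatase, LDH, bilirubin, AST and ALT. With 48 women randomized and one on-study draw, there are at most 48 × 7 = 336 scheduled results. At 2:1 that is 32 × 7 = 224 on vaccine and 16 × 7 = 112 on control. The documents do not say how many would be abnormal or unresolved.

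4. **Distance to the 13.1 limit.** The denominator of the 10% is not stated. Reading it as the share of women with a qualifying event is an assumption, so a range is shown:
   - 48 × 2/3 = 32 vaccinated: 3/32 = 9.4% passes, 4/32 = 12.5% fails.
   - 27 evaluable on vaccine: 2/27 = 7.4% passes, 3/27 = 11.1% fails.
   - 40 evaluable in all: 4/40 = 10.0% passes, 5/40 = 12.5% fails.
   - 48 randomized: 4/48 = 8.3% passes, 5/48 = 10.4% fails.

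   At the margin one omitted qualifying event changes the result. That is true of any omitted event under any threshold, so it shows what one missed event could do and says nothing about how likely this wording is to cause one.

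**The case against.** The best defence is that the two instructions can be read together. Follow-up of an unknown value is advised where possible and is not compulsory. The second condition applies only to an abnormality whose degree requires active management. On that reading a value not yet interpretable is watched, and a value that demands action is reported. The rule also defers a value: once it is judged significant it becomes an AE, and AEs are assessed again at the final visit (7.5).

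Part of this stands. The wording is softer than a strict prohibition paired with a strict duty, and a careful site could find a workable line. But the examples of active management are nearly the same activities that the preceding sentence asks for in unknown values, and the closing sentence drops the qualifier about degree. The line is left to each physician.

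A reader might go further and infer that open grade III/IV lab toxicity will drop out of the go/no-go decision. The documents do not support that:
- Entry requires chemistry below 2 × ULN, platelets of at least 100,000/mm³ and haemoglobin of at least 10 g/dL (4.1.5). A severe on-study value would normally be a worsening that suggests organ toxicity, which is the first condition.
- The general guide in 11.1.3 describes grade 3 as severe or medically significant and grade 4 as calling for urgent intervention. That guide is for AEs without their own CTCAE term and is not itself a trigger for reporting labs, but it points the same way.
- Grade III counts in 13.1 only if attributed to the active drug. A value attributed to the vaccine is already suspected toxicity, so it sits poorly with a label of unknown significance.
- The prior-trial toxicities described in 2.3 and 6.2 are local, constitutional and hypersensitivity reactions, with no lab toxicity mentioned.

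Nor do the documents show that counts will differ by arm. Open-label judgement makes it possible, no more.

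**Conclusion.** The inconsistency in section 11 is real and other sections do not resolve it. Followed literally, the not-reported sentence leaves out some labs that the same section makes reportable. The expected consequence is under-counting and uneven counting in the toxicity profile, mainly of lower-grade or isolated abnormalities, which do not enter the 13.1 rule. Omission of a grade III/IV value from that rule cannot be excluded, because section 11 makes no exception by grade, but it is unlikely because such values normally meet one of the two conditions.

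The size is unknown. It is bounded by one scheduled on-study draw, at most 336 results if all 48 women reach surgery, plus any unscheduled tests. No sample size, power or alpha figure is affected. The conclusion rests on the text alone. Only the threshold illustration needs the assumed per-woman reading and denominator. The point is worth correcting because the correction is cheap and toxicity is a named objective, but it does not threaten the trial's main conclusion.

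**What to change.** The changes concern reporting and analysis only. Management of participants is untouched.

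1. **Section 11.** Take unknown significance out of the sentence listing labs that are not reported. Deleting the phrase alone would leave the category without a stated status, so add that an abnormality under further investigation or added follow-up is recorded as an AE with its grade and updated when the determination is made. Say also that a value still unresolved at the 30-day post-op visit stays as recorded.

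2. **Sections 13.5 and 13.7.** Add a by-arm table of grade shift from baseline to the pre-surgery draw for the seven tests taken at both times, where a CTCAE grade applies, whatever the significance call. Use it as a check on the AE-based grade III/IV count in 13.1.

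The cost is a short text amendment, a few more AE lines (some later found benign) and one extra table. The draws are already scheduled. The documents do not say whether the numerical results are captured on a CRF; if they are not, a field is needed.
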